Correlation and Comparison of the HepQuant® Disease
Severity Index (DSI) With Hepatic Venous Pressure
Gradient (HVPG)

NCT02523196

Protocol Version: August 11, 2015

Protocol #: 15-0520

Project Title: Correlation and comparison of the HepQuant® Disease Severity Index (DSI) with Hepatic Venous Pressure Gradient (HVPG)

Principal Investigator: [name].

Version Date: August 11th, 2015

I. Hypotheses and Specific Aims:

Hypothesis

The HepQuant® (HQ)-SHUNT test is an appropriate alternative to Hepatic Venous Pressure Gradient (HVPG) testing.

Specific Aims

HQ-SHUNT is safe, simple to administer, noninvasive, cost-effective, and well tolerated by patients. In order to prove that the HQ-SHUNT test is an appropriate alternative to measurement of HVPG we will conduct a head-to-head comparison of HQ-SHUNT to HVPG. In this study, 100 consecutive patients with various etiologies of liver disease who have undergone technically successful HVPG testing will subsequently undergo HQ-SHUNT testing.

Primary Aim 1: Create the ROC curve of the Disease Severity Index (DSI) from HQ-SHUNT for defining patients with (HVPG ≥ 6 mmHg) and without (HVPG < 6 mmHg) portal hypertension. From the ROC, define the optimal cutoff of DSI and the sensitivity, specificity, and positive and negative predictive values.

Primary Aim 2: In patients with portal hypertension (HVPG ≥ 6 mmHg), define the optimal relationship of DSI to HVPG.

Exploratory Aims

Approximately 90% of patients undergoing HVPG will have liver biopsy performed as part of the procedure. In addition, most of the patients undergoing HVPG will have undergone or will undergo upper gastrointestinal endoscopy (EGD) to evaluate for varices and variceal treatment. This allows a head-to-head comparison of DSI from HQ-SHUNT with HVPG in identifying patients with cirrhosis and patients with varices. Finally, we will also compare the tolerability of both HVPG and HQ-SHUNT, since tolerability of procedures is critical for patient acceptance and the ability to perform serial testing.

Exploratory Aim 1: Compare the cutoffs of DSI 16.5 and HVPG 6 mmHg in identifying patients with cirrhosis.

Exploratory Aim 2: Compare the cutoffs of DSI 20 and HVPG 10 mm Hg in identifying patients with varices.

Exploratory Aim 3: Survey patients on their experience of having both HQ-SHUNT and HVPG procedures.

II. Background and Significance:

The Clinical Problem in Liver Disease Assessment and Liver Disease Drug Development

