Both HVPG and HQ-SHUNT results correlate with fibrosis stage, prevalence of cirrhosis, and the prevalence and size of varices [7], [8], [9]. DSI appears to have a better and more linear correlation with fibrosis, and more sensitivity at lower fibrosis stages than HVPG (Fig. 3). However all the results summarized above were from separate studies and the two methods have never before been compared in a head-to-head fashion.

IV. Research Methods

A. Outcome Measure(s):

The following outcome measures will be assessed for each Specific Aim:

Primary Aim 1. Two measurements will be compared, HVPG and DSI. The HVPG test results will define the patients with portal hypertension (HVPG ≥ 6 mmHg). DSI will be determined from the HepQuant (HQ)-SHUNT test and the DSI cutoff for portal hypertension will be defined from ROC analysis.

Primary Aim 2. Two measurements will be compared, HVPG and DSI. The relationship between these measurements, in the patients with portal hypertension, will be analyzed by linear and nonlinear regression.

Exploratory Aims:

Exploratory Aim 1. The outcome measure is cirrhotic fibrosis score on liver biopsy. Prevalence of cirrhosis will be determined for cutoffs of DSI 20 and HVPG 6 mmHg.

Exploratory Aim 2. The outcome measure is medium to large varices at EGD. Prevalence of varices will be determined for cutoffs of DSI 20 and HVPG 10 mmHg.

Exploratory Aim 3. The outcome measure is patient tolerability for testing procedures defined by the Patient Survey.

B. Description of Population to be Enrolled:

Inclusion Criteria

- Liver disease patient scheduled to have an Hepatic Venous Pressure Gradient (HVPG) procedure
- At time of enrollment, being between the ages of 18 and 75

Exclusion Criteria

- Concomitant treatment with both a beta blocker and an ACE inhibitor
- Concurrent hepatic malignancy. Patients with a history of treated HCC can be included if there is no evidence of recurrent disease at the time of this study.
- Unstable angina or history of myocardial infarction or congestive heart failure within 6 months prior to enrollment into this study
- Renal insufficiency with chronic kidney disease stage 4 or 5 (GFR < 30 mL/min/1.73m²)
- Crohn's disease or any active intestinal inflammatory condition
- Having had an ileal resection
- Diabetic Gastroparesis
- Pregnancy or intent to become pregnant. Urine pregnancy tests will be performed prior to HQ SHUNT testing.
- Inability to consent for one's self

Stopping Criteria

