This will be done according to the standard of care of the Radiology department performing the procedure. All HVPG (mmHg) measurements will be recorded. In addition, if liver biopsy is obtained, the reading of the biopsy will be the standard of care reading by the Clinical Pathology department. The pathological diagnosis, inflammation score, steatosis score, and fibrosis score will be recorded.

HQ-SHUNT

On the day of HQ-SHUNT testing patients will come to the UCH CTSC and receive a physical examination and a review of their medical history. Prior to testing, blood samples will be taken for CBC, complete chemistry profile, and INR. From these clinical and laboratory data the MELD, CTP, and D'Amico scores will be determined from the following:

1. MELD (formula): $MELD\ score = 3.8\ln(bili) + 11.2\ln(INR) + 9.6\ln(creat) + 6$
2. CTP (table):

	1 Point	2 Points	3 Points
Bilirubin, total (mg/dL)	<2	2 to 3	>3
PBC/PSC	<4	4 to 10	>10
INR	<1.7	1.7 to 2.3	>2.3
Albumin (g/dL)	>3.5	2.8 to 3.5	<2.8
Ascites	None	Responsive	Unresponsive
Encephalopathy	None	Responsive	Unresponsive

NOTE: CTP class A: 5 or 6; CTP class B: 7 to 9; CTP class C: 10 to 15

3. Cirrhosis Stage [10]:
 - a. 1 = Compensated cirrhosis without varices or ascites
 - b. 2 = Compensated cirrhosis with varices
 - c. 3 = Bleeding varices without other disease complications
 - d. 4 = First nonbleeding decompensating event
 - e. 5 = Any second decompensating event

HQ-SHUNT Testing

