
the d4-Cholate dose / d4-Cholate AUC and the Portal HFR is the Oral Clearance normalized to patient weight (mL/min/kg). The concentration of d4-Cholate (μM) at 60 min was found in previous studies to exhibit a reasonable correlation ($r^2 = 0.88$) with Portal HFR so this single blood sample will also be evaluated as a simplified testing approach. The cholate shunt fraction is calculated as $100\% \times \text{Systemic HFR} / \text{Portal HFR}$. The DSI is calculated as $5.34 (\text{SHUNT}) - 6.65 (\text{Lne Portal HFR}) - 8.57 (\text{Lne Systemic HFR}) + 44.66$, and varies from ~ 0 in the healthiest liver to ~ 50 at liver failure.

SURVEY OF PATIENT TOLERABILITY

After undergoing both procedures, at the completion of the HQ-SHUNT test (always the last test), the patients would then be given two surveys, one for HVPG and another for HQ-SHUNT. The purpose of these surveys is to have the patient record their experiences with each procedure as regards their pain, discomfort, inconvenience, and willingness to undergo the procedures again. The two surveys are very similar but are nuanced for the type of testing.

D. Description, Risks and Justification of Procedures and Data Collection Tools:

Only patients who are already scheduled to have an HVPG procedure as part of their standard-of-care will be recruited to participate in this study. Most of these patients will also have liver biopsy either prior to or at the time of the HVPG procedure. In addition, these patients often undergo esophageal endoscopy procedures as part of their standard-of-care. While we will collect the data from these procedures, the subjects will not be exposed to any additional risks from these procedures beyond those associated with these standard-of-care procedures. Neither biopsy nor EGD are requirements for enrollment into this study of HVPG and HQ-SHUNT. The only additional risks will be those incurred from the HQ-SHUNT test.

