Correlation (R) is the assumed sample correlation.
Width if R = 0.0 is the maximum width for a confidence interval with sample size N.

For the linear regression analysis, a sample size of 50 achieves 80% power to detect a change in slope from 0 under the null hypothesis to 0.50 under the alternative hypothesis when the standard deviation of DSI is 3, the standard deviation of HVPG is 4.00, and the two-sided significance level is 0.05.

General Statistical Analysis

Primary Aim 1. It is expected that both HQ-SHUNT results and HVPG measurements will reflect the extent of liver disease. Higher pressures will in general be associated with lower Systemic HFR and Portal HFR, and with higher SHUNT and DSI. The performance of DSI to identify patients with portal hypertension (HVPG ≥ 6 mmHg) will be determined by ROC analysis. Optimal DSI cutoff, sensitivity, specificity, PPV, and NPV will be defined.

Primary Aim 2. We will develop models of the relationships of HQ-SHUNT test results to the HVPG test results based on correlations. We expect there to be a linear relationship for HVPG pressures between 6 and 25 mmHg (i.e. in patients with portal hypertension) and will assess the correlation (with 95% confidence intervals) for HVPG vs. DSI in the 50 patients expected to have HVPG pressures ≥ 6 mmHg. Linear regression will be used to assess the relationship between these variables, taking other covariates into account, and R^2 values will be reported.

Exploratory Aims:

Exploratory Aim 1. It is expected that both HQ-SHUNT results and HVPG measurements will, in general, reflect the extent of liver disease, as measured by the liver fibrosis stage and by the D'Amico cirrhosis stage. Regression models will be developed of the relationships of HQ-SHUNT test results to fibrosis stage and to cirrhosis stage. Likewise regression models will be developed of the relationship of HVPG portal pressure to fibrosis stage and to cirrhosis stage. It is expected that correlations will be found similar to those shown in Fig 3, but now demonstrated in the same patient population.

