Exploratory Aim 2. HQ-SHUNT test results will be compared to HVPG test results at identifying patients with all sizes of varices, as well as at identifying just those patients with medium to large varices that require therapeutic intervention, usually banding. These comparisons will be made using ROC curves and their associated c-statistics. The optimum diagnostic cutoffs of each test will be determined from the ROC curves by the Youden index (J statistic). The sensitivity, specificity, PPV, and NPV of each test will be compared at their respective optimum diagnostic cutoffs.

Exploratory Aim 3. For each procedure, HVPG and HQ-SHUNT testing, the patients will report their pain, discomfort, inconvenience, overall experience, and willingness to undergo repeat testing, each on a scale of 1 to 10. The numerical scores of each question will be compared between the HVPG and HQ-SHUNT testing, in terms of mean score, standard deviation, and statistical significance (t-test).

G. Summarize Knowledge to be Gained:

Overall this study will demonstrate whether The HQ-SHUNT test results can generate physiological information on liver disease patients that is as good, or better, than HPVG pressure measurements. A close correlation between HQ-SHUNT test results and HPVG pressure measurements would allow the safer, less invasive, lower cost HQ-SHUNT test to replace HVPG in patient assessment and in clinical trials of new liver disease therapies and therapeutic agents. However the HQ-SHUNT test reports on the systemic clearance, portal clearance, and portal-systemic shunt and provides a more comprehensive picture of the portal circulation than just the portal pressure. For example, the presence of extensive or large collaterals, such as a spleno-renal collateral, should relieve portal pressure, reduce varices, and reduce the HVPG; while, in contrast, HQ-SHUNT would reveal an increase in SHUNT and DSI. In terms of disease severity, HVPG would be falsely low, while HQ-SHUNT would report accurately.

Varices are clinically very serious because they require intervention to prevent internal bleeding. An HVPG > 10 mm HG has been associated with a risk of varices. A DSI > 20 similarly indicates a risk of large varices, ROC c-statistic 0.82, sensitivity 86%, specificity 65%. This study allows a direct comparison in the same patients of the relative ability of HQ-SHUNT and HVPG to identify patients with varices.

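### Exploratory Aim 2 names DSI 20 and HVPG 10 mmHg for varices, but the analysis compares accuracy only at Youden cutoffs chosen and judged in the same patients, without correction

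*Combined protocol and SAP*

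**What the plan says.** Three places in the combined protocol and SAP bear on this aim.

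- **Section I, Exploratory Aim 2:** "Compare the cutoffs of DSI 20 and HVPG 10 mm Hg in identifying patients with varices".
- **Section IV.A, Outcome Measure(s):** the outcome is medium to large varices at EGD, and "Prevalence of varices will be determined for cutoffs of DSI 20 and HVPG 10 mmHg".
- **Section IV.F, General Statistical Analysis, Exploratory Aim 2:** two outcomes are analysed, varices of any size and medium to large varices. "These comparisons will be made using ROC curves and their associated c-statistics". Each test's cutoff is then taken from its ROC curve by the Youden index, and: "The sensitivity, specificity, PPV, and NPV of each test will be compared at their respective optimum diagnostic cutoffs".

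The IV.F text for this aim mentions neither DSI 20 nor HVPG 10. The documents describe one cohort and no split sample, cross-validation, bootstrap correction or validation cohort. Section IV.D adds: "Neither biopsy nor EGD are requirements for enrollment into this study of HVPG and HQ-SHUNT". The number of patients with a varix reference standard is therefore unknown.

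**The concern.** The aim asks how two thresholds fixed in advance perform. The analysis reports how two thresholds perform after each has been tuned to the data in hand. With two varix outcomes and two tests, up to four data-derived cutoffs may be reported, and none need be 20 or 10.

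A Youden cutoff maximises sensitivity plus specificity in the sample, so it partly follows chance features of that sample. Accuracy read off in the same patients is too high on average, though not in every sample. The c-statistics need no cutoff and do not have this problem.

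Two things are at stake. Section IV.G cites sensitivity 86% and specificity 65% for DSI above 20. This study could check those figures in new patients, but only if accuracy is reported at DSI 20. Also, a test on a finer scale offers more candidate cutoffs and gains more from the search, so the comparison itself can tilt.

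**Working it through.** **Inputs from the protocol**

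- DSI > 20 for large varices: c-statistic 0.82, sensitivity 86%, specificity 65% (IV.G), so J = 0.86 + 0.65 − 1 = 0.51.
- HVPG: "the standard deviation of HVPG is 4.00" (IV.F, Power and Sample size, Primary Aim 2). Recording: "All HVPG (mmHg) measurements will be recorded" (IV.C), with no precision given.
- No power or precision figure is given for this aim, so there is none to reproduce.

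**Assumptions not in the protocol:** 20/60, 30/60 or 40/50 patients with/without varices; binormal scores; correlation 0.5 between the tests where both are simulated.

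**Models.** With equal variances the separation is d = √2·Φ⁻¹(0.82) ≈ 1.29, and the largest true J is 2Φ(d/2) − 1 = 0.483. An equal-variance curve through 86%/65% would have AUC 0.85, not 0.82. A second model therefore uses an SD ratio (non-cases to cases) of 1.52, which gives AUC 0.82 and passes through 86%/65%; its maximum J is 0.511.

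**Optimism.** In each of 20,000 samples per setting the Youden cutoff was derived, and apparent accuracy was set against the model's true accuracy at that cutoff. AUC 0.82, equal variance:

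| With/without varices | Sensitivity, apparent vs true | Specificity, apparent vs true | J, apparent vs true | J too high in | PPV, points | NPV, points |
|---|---|---|---|---|---|---|
| 20/60 | 0.789 vs 0.709 | 0.773 vs 0.747 | 0.562 vs 0.456 | 87.5% | +5.9 | +3.1 |
| 30/60 | 0.779 vs 0.719 | 0.771 vs 0.742 | 0.550 vs 0.461 | 86.4% | +5.1 | +3.3 |
| 40/50 | 0.775 vs 0.728 | 0.771 vs 0.734 | 0.546 vs 0.462 | 85.8% | +4.5 | +3.9 |

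Unequal variance, same order:

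- J optimism 0.100, 0.083, 0.077.
- Sensitivity +7.6, +5.6, +4.3 points; specificity +2.4, +2.7, +3.4 points.
- J too high in 87.1%, 84.9%, 84.0% of samples.

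Across AUC 0.72 to 0.90 and both models, J optimism runs from 0.068 to 0.123. With 10/60 at AUC 0.82 it is 0.147 (equal variance) or 0.140 (unequal).

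**Fixed cutoff for contrast.** At AUC 0.82 with 20/80 (8,000 samples), mean observed J at a cutoff set in advance was 0.482 against a true 0.483.

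**Effect on the comparison.** Two tests, both with AUC 0.82, HVPG rounded to whole mmHg with SD 4:

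- Apparent J difference (DSI minus HVPG) 0.031, 0.026, 0.025; true difference 0.002, 0.002, 0.001.
- HVPG's own optimism falls to 0.079, 0.065, 0.060.
- With SD 3 the apparent difference is 0.036, 0.034, 0.032; with SD 5 it is 0.024, 0.022, 0.022.

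**Can prevalence give the missing figures?** With 30/60 and 86%/65%, varix prevalence above the cutoff is 25.8/(25.8 + 21) = 55.1%, and below it 4.2/(4.2 + 39) = 9.7%. These two figures with the overall prevalence return 86%/65%. Prevalence on one side alone does not.

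**Precision at fixed cutoffs.** Exact 95% CIs: 17/20, 62.1% to 96.8%; 34/40, 70.2% to 94.3%; 39/60, 51.6% to 76.9%. With equal AUC 0.82, DSI placed at 86% sensitivity and the other test at its optimum, the true J difference is 0.038:

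- McNemar on sensitivity alone rejects in 5.4%, 13.6%, 22.2% of samples.
- McNemar on specificity alone rejects in 49.4%, 49.2%, 41.9%.
- The paired J difference rejects in 7.3%, 6.8%, 7.0%, with 95% CI coverage of 94.2% to 94.6% and half-widths 0.247, 0.219, 0.211.

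**Do corrections work?** From uncorrected J bias of 0.106, 0.090, 0.086, 10-fold cross-validation repeated five times left −0.0015, −0.0003, 0.0023 (Monte Carlo SE 0.002 to 0.003). Bootstrap optimism subtraction left 0.037, 0.029, 0.029, so it removed about two thirds.

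**The case against.** Section IV.A does use the named cutoffs. If it means prevalence on both sides of each cutoff, PPV and NPV at DSI 20 and HVPG 10 follow directly, and sensitivity and specificity follow once overall prevalence is added. That is a fair reading, but the wording does not settle it, and no paired comparison at those cutoffs is planned anywhere.

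The aim compares two tests, and both receive a tuned cutoff, so most of the optimism cancels. This stands for the difference: the remaining 0.025 to 0.031 is about one eighth of the 0.21 to 0.25 half-width for a fixed-cutoff paired J difference. It depends on whole-mmHg recording, equal AUCs, a correlation of 0.5, and an SD borrowed from the sizing for patients with portal hypertension. It does not rescue each test's own reported accuracy, which carries the full overstatement.

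The group sizes are assumed and the aim is exploratory. Both are true. They limit the weight of the point but do not remove the mismatch between aim and analysis. Cross-validation may also look heavy when 20 cases leave about two per fold, yet the repeated version removed the bias in that setting.

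**Conclusion.** The point holds and should be corrected. Beyond the c-statistics, the stated analysis reports accuracy only at cutoffs tuned to the same patients, and it does not explicitly report accuracy for the comparison that the aim names.

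Under the assumed group sizes and AUC 0.82, J is overstated on average by 0.08 to 0.11, sensitivity by 4 to 8 points, specificity by 2 to 4, PPV by 4 to 6 and NPV by 3 to 4. With only 10 cases the J overstatement is 0.14 to 0.15. The tilt towards DSI is small and conditional on whole-mmHg HVPG. The c-statistic comparison stands, and no primary conclusion or sample size is affected.

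**What to change.** In section IV.F, Exploratory Aim 2, for the varix outcomes already planned and in patients with an EGD:

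1. Report sensitivity, specificity, PPV and NPV at DSI 20 and HVPG 10 with exact 95% CIs, and paired differences with 95% CIs. State whether each cutoff is strict; section IV.G writes both with a greater-than sign.
2. Read sensitivity and specificity together through the paired difference in J. A McNemar test on either alone can reflect only where a threshold sits.
3. Keep the c-statistic comparison and name a paired test for it, such as DeLong.
4. Label the Youden results exploratory and give repeated 10-fold cross-validated estimates beside the apparent ones.
5. In section IV.A, say whether prevalence is reported on both sides of each cutoff.

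The cost is plan wording and a little more analysis of data already collected. Reported accuracy will look less favourable, and the fixed-cutoff estimates will be imprecise if few patients have varices or an EGD.

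### Exploratory Aim 2 compares DSI and HVPG index by index at separately sample-picked Youden cutoffs, so the result partly reflects where each cutoff falls and not which test better identifies varices

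*Combined protocol and SAP*

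**What the plan says.** Section IV.F (General Statistical Analysis, Exploratory Aim 2) sets HQ-SHUNT against HVPG for detecting varices of any size and, separately, medium to large varices. It plans two kinds of comparison:

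- One that needs no cutoff: "These comparisons will be made using ROC curves and their associated c-statistics".
- One at cutoffs. Each test's optimum is read off the study's own ROC curve by the Youden index, and then: "The sensitivity, specificity, PPV, and NPV of each test will be compared at their respective optimum diagnostic cutoffs".

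It does not say which of the two leads. For the four indices it names no test, paired method, matched specificity or resampling of the cutoff choice.

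Elsewhere the same aim is stated with fixed cutoffs. Section I has "Compare the cutoffs of DSI 20 and HVPG 10 mm Hg in identifying patients with varices", and section IV.A has "Prevalence of varices will be determined for cutoffs of DSI 20 and HVPG 10 mmHg". The analysis text in IV.F does not use them.

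Section IV.G gives the purpose: "This study allows a direct comparison in the same patients of the relative ability of HQ-SHUNT and HVPG to identify patients with varices". It also quotes earlier results for DSI above 20 and large varices: c-statistic 0.82, sensitivity 86%, specificity 65%.

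**The concern.** The question is relative ability to identify varices, so the natural null is equal discrimination. A comparison of sensitivity with sensitivity and specificity with specificity, each test at its own sample-chosen point, has a different null: that both tests sit at the same operating point. Near the Youden optimum, sensitivity can be traded for specificity at almost no loss in the index, so chance decides where each test lands. One test may come out sensitive and unspecific and the other the reverse, even when the two true ROC curves coincide.

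This is separate from the optimism of a single selected cutoff. Both tests are optimised in the same way here, and the gap between them on any one index can still mislead. At stake is a report that ranks DSI above or below HVPG on sensitivity, specificity, PPV or NPV when the tests are equally accurate.

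**Working it through.** **Inputs from the documents.** AUC 0.82 for DSI and large varices (IV.G); "100 consecutive patients with various etiologies of liver disease" (section I), with both tests in each patient; HVPG standard deviation 4 mmHg (IV.F), used only in a rounding check.

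**Assumed, because the documents give no figure.** 60 to 100 patients with endoscopy; 20% to 40% with varices; within-group correlation between tests 0.3 to 0.6; HVPG with the same AUC as DSI; normal scores with equal variance.

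**1. The plan's nearest ROC figure.** Exploratory Aim 2 states no power. Primary Aim 1 states 80% power with 50 + 50 patients, AUC 0.65 against 0.7945. I used the large-sample Hanley-McNeil variance, V(A) = A/(2−A) − A² + 2A²/(1+A) − A².

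- V(0.65) = 0.1486 and V(0.7945) = 0.1001.
- N per group = (1.96·√0.1486 + 0.8416·√0.1001)² / 0.1445² = 50.01.

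The figure reproduces, and nothing below disputes it.

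**2. How flat the curve is.** For equal-variance normal scores, the separation is d = √2·z(0.82) = 1.4142 × 0.9154 = 1.2945. Sensitivity = Φ(d − z(specificity)), and J = sensitivity + specificity − 1.

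| Specificity | Sensitivity | J |
|---|---|---|
| 0.60 | 0.851 | 0.451 |
| 0.65 | 0.818 | 0.468 |
| 0.74 | 0.743 | 0.483 (maximum) |
| 0.80 | 0.675 | 0.475 |
| 0.85 | 0.602 | 0.452 |

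From specificity 0.65 to 0.80, sensitivity falls by 14 points while J stays within 0.015 of its maximum. In simulated samples of 80 to 100, one test's Youden-point sensitivity runs from about 0.6 to 0.94 (5th to 95th percentile).

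**3. Two equally accurate tests in the same patients.** Each simulated study was analysed at each test's own sample Youden cutoff, and at a cutoff fixed in advance at the same ROC point. Ranges over the assumed settings:

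| Result in a study | Own Youden cutoffs | Common fixed cutoff |
|---|---|---|
| One test ≥10 points better on sensitivity and ≥10 points worse on specificity | about 29% to 39% | 1% to 5% |
| Exact McNemar p < 0.05 on sensitivity or specificity | about 25% to 44% | 2% to 6% |
| Sensitivity gap ≥10 points, taken alone | 45% to 65% | 20% to 55% |
| Gap ≥10 points in sensitivity + specificity | 26% to 51% | 34% to 59% |

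One setting in full (80 patients, 40% with varices, correlation 0.5, 2,000 runs), Youden against fixed:

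- opposite 10-point gaps, 34.0% against 2.2%;
- McNemar, 33.0% against 5.1%;
- correlation between the sensitivity and specificity differences, −0.79 against −0.03.

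That negative correlation is the mark of cutoff placement.

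**4. PPV and NPV.** With 80 to 100 patients, 30% to 50% with varices and correlation 0 to 0.8, PPV gaps of 10 points or more occur in 18% to 42% of studies (fixed cutoff 3% to 26%). NPV gaps of that size occur in 3% to 26% (fixed 0.5% to 15%).

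**5. Other assumptions.** The McNemar rate at Youden cutoffs is 47% at AUC 0.75, 26% at AUC 0.90, 46% with 15% varices, and 35% with HVPG rounded to 1 mmHg.

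**6. The alternatives on equal-accuracy data.** The paired DeLong test on c-statistics rejects in 3.6% to 6.1% of runs. Sensitivity at a common specificity of 0.75, with a bootstrap that re-derives both cutoffs, rejects in 2.5% to 4.3% (400 runs per setting). At a common specificity of 0.65, one setting gave 2.2% (500 runs).

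**The case against.** The strongest reply is that the plan names no test and makes no superiority claim for these four indices. The next paragraph, Exploratory Aim 3, does name a t-test, so the comparison in Aim 2 may be meant as descriptive. That stands. A reader might infer that the plan will declare false significant differences in a quarter or more of studies. The documents do not support this, and the McNemar rates apply only if such a test were used. The opposite 10-point gaps depend on no test.

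Further points that stand:

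- Raw 10-point gaps in sensitivity are largely ordinary sampling error. With 20% varices and correlation 0.3 they occur in 47% against 42%, 56% against 50% and 64% against 54% of studies (Youden against fixed cutoff). The excess is larger with 40% varices: 45% against 27% at 80 patients.
- Read jointly, sensitivity plus specificity shows no excess difference. The artefact is a trade-off, visible to anyone who reads both indices.
- The c-statistic comparison in the same paragraph is sound, so Aim 2 as a whole is not invalid.
- A reader might infer that section IV.G rests its judgement on the Youden-point comparison. It does not mention Youden cutoffs; the sentence on direct comparison follows HVPG above 10 and DSI above 20.
- Performance at each test's own best cutoff is a legitimate thing to report.

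These points limit the concern but do not remove it. The plan still prespecifies an index-by-index comparison, gives it no lower rank than the c-statistics, and does not say what to conclude if the two disagree. The fixed cutoffs in sections I and IV.A would avoid sample-picking, but they need not lie at the same ROC point, and IV.F does not use them.

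**Conclusion.** The concern holds in a limited form. Comparing the four indices at separately sample-picked Youden cutoffs partly measures cutoff placement. Under equal accuracy the two tests are split in opposite directions by 10 points or more in about three to four studies in ten, against at most one in twenty at a common fixed cutoff.

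The size rests on the assumed endoscopy numbers, varices prevalence, between-test correlation, equal AUC and normal scores. The model is approximate: it gives 82% sensitivity at 65% specificity, where the protocol quotes 86%. The direction held in every setting tried.

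The flaw is confined to conclusions drawn from single indices. Because the aim is exploratory and the primary aims are untouched, severity is low.

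**What to change.** In section IV.F, Exploratory Aim 2:

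1. State that the paired c-statistic difference (DeLong, same patients) with its 95% CI carries the DSI versus HVPG comparison.
2. Add a comparison of the two sensitivities at one common specificity fixed in advance (for example the 65% quoted for DSI in IV.G). Give a paired bootstrap CI that re-derives both cutoffs in each resample.
3. Report each test's Youden cutoff and its four indices descriptively, and draw no between-test conclusion from a single index.
4. Reconcile this text with the cutoffs DSI 20 and HVPG 10 mmHg that sections I and IV.A name for the same aim. Say what role each analysis has, and note that the two fixed cutoffs may sit at different ROC points.

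The cost is a few sentences of analysis plan and a short bootstrap routine, with no new data. The matched-specificity interval will be wide and somewhat conservative at this sample size, so fewer differences will be claimed.
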